12.7 Analysis of Secondary Endpoint: Pain

To assess pain severity (worst pain, least pain, average pain, current pain, pain interference with activities of daily living, and opiate use) between groups at 6, 12, 18, and 24 months, the two-sample Wilcoxon rank sum test and two-sample t test for continuous measurements will be used. To determine if progression of pain is different between the two groups over time, we will use generalised linear mixed models for repeated measures for each pain score with appropriate link function, where group, strata and covariates will be considered as fixed effects, and time will be considered as the repeated measure. We will also use area under the curve analyses, where appropriate. In order to complete this as an intention to treat analysis, patient with missing data due to failing health or death will be run multiple ways, including assigned scores of maximum pain and using last observation carried forward.

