- Experiences shortness of breath, chest discomfort, or palpitations when performing activities of daily living (patient with these symptoms can participate in the study with cardiologist clearance)
- Ongoing restriction of physical activity with physician documentation
- Has chest pain brought on by physical activity (patient can participate in the study with cardiologist clearance)
- Has developed chest pain in the past month (patient can participate in the study with cardiologist clearance)
- Moderate-to-severe bone pain (i.e., National Cancer Institute's Common Terminology Criteria for Adverse Events grade 2-3 bone pain).
- Men who do not complete the baseline lifestyle and quality-of-life questionnaires and 3-days of diet diaries or country-specific FFQ will not be eligible

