12.8 Analysis of Secondary Endpoint: Circulating Metabolic Biomarkers

Positively skewed variables will be log transformed prior to analyses. Graphical methods will be used in the first instance to show trends over time and differences between the intervention and control groups using box plots or line graphs. To test for differences between the intervention and control group, we will use two-sample *t*-tests with the assumption of unequal variance to compare baseline, 6, 12, and 24 month circulating inflammatory and energy metabolism biomarker levels, as well as mean changes and effect sizes in these measurements over the study period. Where differences are seen, these will be further investigated within the intervention group against compliance to exercise to demonstrate a dose response relationship. Biomarker assessment at baseline and 6 months are funded. Additional funding will be acquired for investigation of additional time points.

We will also calculate absolute changes in circulating inflammatory and energy metabolism biomarker levels, and use *t*-tests to test the null hypothesis that the average change in these measurements in the control and exercise groups is zero. We will use multivariate linear regression to examine the effect of the intervention on change in inflammatory and energy metabolism biomarker levels at 6, 12, and 24 months, adjusting for baseline levels. Additionally, to examine changes in metabolic biomarkers at various time points during the study period, we will utilise a mixed effects model with adjustment for baseline biomarker levels. Treatment assignment and time (6, 12, 24 months) and treatment × time interaction will be included as fixed effects. Biomarker assessment at baseline and 6 months are funded. Additional funding will be acquired for investigation of additional time points.

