12.9 Analysis of Secondary Endpoint: Physical Function

To examine strength levels (kilograms lifted for chest press, leg press, seated row and leg extension), cardio-respiratory exercise capacity (oxygen consumption and workload achieved), and functional performance (time in seconds to complete 400m walk test) between groups at 0, 6, 12, 18 and 24 months when performed, the two-sample Wilcoxon rank sum test and two-sample t-test for continuous measurements will be used. To determine if changes in strength, cardiorespiratory exercise capacity and functional performance is different

between the two groups over time, we will use generalised linear mixed models for repeated measures, where group, strata and covariates will be considered as fixed effects, and time will be considered the repeated measure. In order to complete this as an intention to treat analysis, patients with missing data due to failing health or death will be run multiple ways, including assigned levels of physical function across metrics described, and using last observation carried forward.

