12.10 Analysis of Secondary Endpoint: Quality of Life

To assess QOL scores (overall QOL, physical wellbeing, social/family wellbeing, emotional wellbeing, functional wellbeing, prostate specific concerns, fatigue, health status) between groups at 6, 12, 18, and 24 months, the two-sample Wilcoxon rank sum test and two-sample t test for continuous measurements will be used. To determine if the change in QOL is different between the two groups over time, we will use generalised linear mixed models for repeated measures for each QOL score with appropriate link function and group, strata and covariates considered as fixed effects, and time considered as the repeated measure. For the EQ5D analyses (QOL utility), we will compare area under the curve. We will consider one value set and country-specific value sets. In the absence of a country-specific value set, a set of values for a population that most closely approximates that country will be used. In order to complete this as an intention to treat analysis, patient with missing data due to failing health or death will be run multiple ways, including assigning scores of zero quality of life and using last observation carried forward.

[figure not shown]

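### Pain, physical function and QOL: the only stated visit-by-visit comparisons ignore baseline and name no deciding test, and the mixed models leave their covariates unspecified

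*Combined protocol and SAP*

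**What the plan says.** Three sections share one structure.

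- **Pain (12.7):** at 6, 12, 18 and 24 months, "the two-sample Wilcoxon rank sum test and two-sample t test for continuous measurements will be used".
- **Physical function (12.9):** the same pair of tests, "between groups at 0, 6, 12, 18 and 24 months when performed".
- **Quality of life (12.10):** "between groups at 6, 12, 18, and 24 months, the two-sample Wilcoxon rank sum test and two-sample t test".

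Each section then adds a generalised linear mixed model for repeated measures to address change over time. In 12.7 the model is one "where group, strata and covariates will be considered as fixed effects, and time will be considered as the repeated measure"; 12.9 and 12.10 are worded almost identically. The covariates are not listed, the baseline score is not named, and no group-by-time interaction appears.

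Section 12.8 (biomarkers) is more explicit. It has a regression for change in "biomarker levels at 6, 12, and 24 months, adjusting for baseline levels", and a baseline-adjusted mixed model with treatment, time and their interaction. It also runs raw two-sample t-tests, including one at baseline.

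Baseline values are collected:

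- Section 3.2 makes ineligible "Men who do not complete the baseline lifestyle and quality-of-life questionnaires".
- Section 5.4 places the BPI-SF at screening.
- Section 5.2 uses the screening CPET as the baseline result and schedules the 400m walk and 1RM tests at Cycle 0.

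**The concern.** There are two separate problems.

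1. **Precision.** A follow-up score compared without the man's own baseline carries all the between-man variation that baseline would explain. The data to remove it are already in hand, and the plan does remove it for biomarkers.
2. **Which result counts.** Two tests are named for each score and visit with no rule for choosing. In 12.9 every outcome is continuous, so both tests fall on the same measure. Section 4.6 relies on a blinded statistician running analyses specified in advance, because patients and staff are unblinded. A choice between two tests is not fully specified in advance.

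The month-0 comparison in 12.9 adds nothing. Those values are taken before the man learns his arm (Table 1, footnote 2), so it tests the randomisation and not the intervention.

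What is at stake is the precision and clarity of the answers to objectives 2.4 (degree of pain and opiate use) and 2.7, and to the physical-function endpoint.

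**Working it through.** **The plan's own figures.** No power or sample size is stated for these endpoints. The nearest figures are the function thresholds in section 12.12, and they reproduce: 0.40 × 5.16 kg = 2.06 kg and 0.40 × 8.75 s = 3.5 s.

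**Number of comparisons, read literally.**

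- Pain: 6 measures × 4 visits = 24.
- QOL: 8 scores × 4 visits = 32.
- Function: 5 measures × 5 visits + 2 CPET measures × 3 visits (Table 1) = 31.
- Total: 87 comparisons, or 80 without month 0. Two tests each give 160 post-baseline p-values.

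**Gain from baseline adjustment.** The variance of the adjusted difference is (1 - r²) times the raw variance, so effective n rises by 1/(1 - r²). Power is Φ(d√(n/2)/√(1 - r²) - 1.96). The documents do not give r. I also assume n = 250 per arm and d = 0.2 SD for illustration. Raw power is Φ(0.2 × √125 - 1.96) = 60.9%.

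| r (assumed) | Effective n factor | Power |
|---|---|---|
| 0.2 | 1.04 | 62.6% |
| 0.3 | 1.10 | 65.0% |
| 0.4 | 1.19 | 68.4% |
| 0.5 | 1.33 | 73.3% |
| 0.6 | 1.56 | 79.8% |
| 0.7 | 1.96 | 87.9% |
| 0.8 | 2.78 | 96.1% |

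**Function at the plan's effect size.** With d = 0.40 in SDs of the score and 250 per arm, raw power is Φ(0.40 × √125 - 1.96) = 99.4%, which leaves almost nothing to gain. One caution: section 12.12 describes its SDs as SDs of change, and gives them only for the 400m walk and leg extension. If the effect is 0.40 SD of change, it equals 0.40 × √(2 - 2r) score SDs. At r = 0.8 that is 0.253, and raw power is 80.7%.

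**When deaths receive a worst score.** One planned version assigns maximum pain (12.7) or zero QOL (12.10) for failing health or death. Under the section 12.2 assumptions (exponential, median 33.5 months, HR 0.78), deaths by 24 months are 1 - 2^(-24/33.5) = 39% in control and 1 - 2^(-0.78 × 24/33.5) = 32% in intervention. Suppose 35% are assigned a score k SDs from the survivors' mean, unrelated to baseline. The squared correlation with baseline becomes 0.65r²/(1 + 0.35k²).

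- k = 2, r = 0.8: 0.416/2.4 = 0.173, factor 1.21.
- k = 4, r = 0.4: 0.104/6.6 = 0.016, factor 1.02.

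So for r of 0.4 to 0.8 and k of 2 to 4, the gain shrinks from 1.19–2.78 to 1.02–1.21.

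**Two tests, no deciding one.** I used 20,000 null simulations with 200 per arm; the distributions are assumptions.

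| Distribution | Either test p < 0.05 | Tests disagree |
|---|---|---|
| Normal | 6.1% | 2.0% |
| Zero-heavy 0–10 score | 6.9% | 4.2% |
| Log-normal | 7.9% | 6.1% |

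**The case against.** **The mixed model may already use baseline.** A reader might infer that these endpoints receive no baseline adjustment anywhere. The documents do not support that. The covariates in 12.7, 12.9 and 12.10 are unnamed, so baseline may be among them, and in 12.9 month 0 could enter the model as an outcome. Absence of adjustment is established only for the visit-wise tests. What remains is that the model is unspecified and, lacking a group-by-time term, does not as written yield an arm difference at each visit.

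**The raw tests are not wrong.** In a 1:1 randomised comparison the unadjusted t test is valid and unbiased. This stands: the loss is efficiency.

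**Section 12.8 is not a clean template.** This also stands. It too starts with raw t-tests, including at baseline; only its adjusted model is the precedent.

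**Two p-values is one reading.** The phrase about continuous measurements could attach to the t test alone, leaving the Wilcoxon test for ordinal items such as the 0–3 analgesic score. No such rule is written, and the reading is weak in 12.9. Nor does the plan say that the smaller p-value will be reported, so 6 to 8% is what would follow from doing so, not the plan's error rate.

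**The gain may be small.** Excluding moderate-to-severe bone pain (3.2) narrows baseline pain and makes a high r less plausible there. 1RM tests may be omitted by metastasis site (5.2.3, Table 2), so baseline strength is not complete. Worst-score data are strongly two-peaked, which favours a rank test for that version. All three points are accepted.

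**Conclusion.** The point holds for the visit-by-visit comparisons. They ignore an available baseline score and name no deciding test, and the models beside them do not say whether baseline is a covariate.

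The effective sample size forgone is a factor of 1.04 to 2.78 for r of 0.2 to 0.8. It is roughly 1.02 to 1.21 where about a third of men are assigned a worst score, for r of 0.4 to 0.8. For function it is of little consequence if an effect of 0.40 SD of the score holds at about 250 per arm. The correlation, the 250 per arm, the 0.2 SD and the simulated distributions are my assumptions.

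The per-comparison error inflation, about 6 to 8% if the smaller p-value is reported, is modest. The undefined deciding result is the larger issue. These are secondary endpoints, and the overall survival analysis and sample size are unaffected.

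**What to change.** This is a free improvement, not the correction of an invalid analysis.

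1. In 12.7, 12.9 and 12.10, name one deciding analysis for each score: the repeated-measures model with baseline score, strata, group, time and group-by-time, read out as the arm difference at each visit.
2. Keep the visit-wise Wilcoxon test as supportive. For the version that assigns worst scores for death, use a rank-based comparison.
3. List the remaining covariates, and say how a man without a baseline 1RM value is handled.
4. Delete the between-arm test at month 0 in 12.9, and likewise the baseline t-test in 12.8.

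The cost is wording in the statistical section. It needs no new data, visits or patients, and should be settled before outcome data are examined by arm.

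### Sections 12.7, 12.9 and 12.10 state no group-by-time contrast and no primary handling of death, and nothing stops their carry-forward run at death

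*Combined protocol and SAP*

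**What the plan says.** **The question and the model.** Section 12.7 sets its aim as "To determine if progression of pain is different between the two groups over time", and Section 12.10 as "To determine if the change in QOL is different between the two groups over time". Section 12.9 asks the same of strength, cardiorespiratory capacity and the 400m walk. The model in 12.7 is one "where group, strata and covariates will be considered as fixed effects, and time will be considered as the repeated measure"; in 12.9 it is one "where group, strata and covariates will be considered as fixed effects, and time will be considered the repeated measure"; 12.10 lists the same terms. Two-sample t and Wilcoxon tests at each visit are also planned. By contrast, the mixed model in Section 12.8 adjusts for baseline level and includes treatment, time and their interaction.

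**Death.** All three sections treat data missing through failing health and through death together and analyse them in several ways:

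- 12.7: "including assigned scores of maximum pain and using last observation carried forward"
- 12.9: "including assigned levels of physical function across metrics described, and using last observation carried forward"
- 12.10: "including assigning scores of zero quality of life and using last observation carried forward"

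No run is named primary. Section 12.9 does not say what level is assigned.

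**EQ-5D.** Section 12.10 says: "For the EQ5D analyses (QOL utility), we will compare area under the curve". Section 5.4 describes the QALY as quality-adjusted survival, and Section 12.1 lists QOL-adjusted OS as a secondary endpoint.

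**The concern.** A model whose only treatment term is group gives one difference averaged over visits. That does not answer whether the arms change differently. If no interaction test or visit contrast is named, the choice can be made after the results are seen. The by-visit tests compare levels, not change.

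Carrying a score forward past death credits a dead man with his last living pain, function or utility. If one arm has more deaths, it receives more of this credit. For an EQ-5D area meant to reflect survival as well as quality, that removes the part of the difference that comes from survival. The assigned-score run treats death in the opposite way, so the two runs can disagree in size or conclusion, and the plan does not say which one governs. In 12.9 the assigned-score run cannot be carried out from the text, because no level is given and a walk time has no natural worst value.

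**Working it through.** **1. The plan's own figure.** Section 12.2 gives exponential survival, control median 33.5 months, hazard ratio 0.78, 80% power, 0.05 (two-sided in 12.4), 36 months' enrolment and 36 months' minimum follow-up.

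- Monthly hazards: ln 2 / 33.5 = 0.02069 (control) and 0.78 × 0.02069 = 0.01614 (intervention).
- Probability of death on study: 1 − [exp(−36λ) − exp(−72λ)] / (36λ) = 0.665 and 0.576.
- N = 2 × (1.960 + 0.842)² × (1/0.665 + 1/0.576) / (ln 0.78)² = 824, as stated.

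The figures below use only the two hazards and do not depend on the enrolment period.

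**2. Deaths by Cycle 24 Day 1.** T = 24 × 28 = 672 days = 22.08 months. Dead = 1 − exp(−λT) = 36.7% control and 30.0% intervention, a gap of 6.70 points. With 433 men per arm that is about 159 + 130 = 289 of 866.

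**3. Time credited after death.** Mean months alive to T = [1 − exp(−λT)] / λ = 17.72 and 18.57, a difference of 0.85. Mean months after death = 22.08 − 17.72 = 4.36 and 22.08 − 18.57 = 3.51. With equal, constant utility u, carry-forward gives every man u × 22.08, so the difference between arms is 0. The size depends on the hazard ratio:

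| Hazard ratio | Gap in % dead | Difference in months alive, cancelled by carry-forward |
|---|---|---|
| 0.78 | 6.7 | 0.85 |
| 0.85 | 4.5 | 0.57 |
| 0.90 | 3.0 | 0.38 |
| 1.00 | 0 | 0 |

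**4. EQ-5D area under the curve.** Visits are at baseline and Cycles 6, 12, 18 and 24 (Section 5.4), with the trapezoid rule between visits. Assumptions, because the documents give no values: the window runs to Cycle 24; utility is 0.7 in both arms; and utility is either constant or falls linearly to 0.4 before death. Section 1.4 does describe quality of life deteriorating as disease advances. No data are missing in living men. Differences between arms at hazard ratio 0.78, in quality-adjusted months:

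| Utility path | True | Carry-forward run | Zero-score run |
|---|---|---|---|
| Constant 0.7 | 0.60 | 0.00 | 0.59 |
| Falls to 0.4 over last 6 months | 0.65 | 0.20 | 0.65 |
| Falls to 0.4 over last 12 months | 0.70 | 0.30 | 0.69 |

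The 0.65 is 0.651 by direct integration; simulated draws give 0.65 to 0.66.

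**5. Other scales.** If living scores are equal in both arms, carry-forward shows no difference at Cycle 24. Assigning maximum pain (10) at death shows 0.0670 × (10 − s) = 0.54 to 0.40 points for an assumed living score s of 2 to 4. Assigning zero on a 0–100 scale shows 0.0670 × s = 4.0 to 5.4 points for s of 60 to 80.

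**6. Model terms side by side.** Section 12.8: baseline, treatment, time, treatment × time. Sections 12.7, 12.9 and 12.10: group, strata and unnamed covariates, with time only as the repeated measure.

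**7. Baseline adjustment of the by-visit comparisons.** The gain in effective sample size is 1/(1 − r²) = 1.10, 1.33 and 1.96 for a baseline correlation r of 0.3, 0.5 and 0.7. These correlations are assumed, so the factor is illustrative only.

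**The case against.** - *The plan does not ignore death.* A reader might infer that the EQ-5D result will be wrong whatever is done. The documents do not support that: 12.10 also plans a zero score, and step 4 shows that this run comes within 0.01 month of the true difference. This stands, and it confines the fault to the carry-forward run and the missing precedence. The match does assume that only death causes missing scores; 12.10 would also give zero to living men in failing health.
- *Carry-forward may never have been meant for the EQ-5D area.* Sections 5.4 and 12.1 point that way. But the sentence on missing data closes the section that contains the area, and it exempts nothing.
- *The model wording may be shorthand.* A repeated-measures model with a stated interest in change may be intended to include visit and its interaction, and the covariates may include baseline. So the text does not establish that the wrong model will be fitted. It does establish that no test of differential change is stated, although 12.8 states one.
- *Two extreme runs bracket the answer.* That is a fair use of sensitivity analyses, but it needs a primary analysis to be sensitive about.
- *The imbalance rests on one hazard ratio.* This stands. It shrinks as the ratio nears 1 and would also shrink if the effect were delayed.

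**Conclusion.** The point holds as a gap in specification plus one faulty run. The three sections state no group-by-time contrast for the question they pose, name no primary handling of death, leave the assigned level in 12.9 undefined, and do not stop carry-forward at death.

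At the planning hazard ratio, carry-forward cancels a 0.85-month difference in time alive to Cycle 24. With assumed utility 0.7, it shows between none and under half of a true 0.60 to 0.70 quality-adjusted months. These sizes rest on exponential survival, an effect present from randomisation, and the assumed window and utilities.

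Three stronger inferences are not supported. Carry-forward does not create a benefit when survival and scores are equal; it can hide one that comes from survival. The unadjusted by-visit tests lose precision but are not biased. OS and its sample size of 824, inflated to 866, are untouched, because only secondary endpoints are involved. The sections should be changed before the analysis.

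**What to change.** 1. In 12.7, 12.9 and 12.10, use the type of model in 12.8, with baseline score, randomisation strata, group, visit and group-by-visit as fixed effects. Name the group-by-visit test or visit contrast that answers the question about change over time. Report the baseline-adjusted visit contrasts as the main by-visit result and keep the rank test as a sensitivity analysis.
2. Carry no score past death. In the EQ-5D area under the curve, set utility to 0 from the date of death and make this the primary EQ-5D analysis.
3. Handle death separately from missing data in living men. Name one primary handling of death for the other scales and say what it estimates: an assigned score is a composite of survival and score, whereas a survivors-only contrast compares selected groups (63.3% v 70.0% alive at Cycle 24). If the assigned-level run in 12.9 is kept, state the level for each measure.

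The cost is analysis wording and a little more analysis work, with some reliance on model assumptions. Baseline scores, visit dates and death dates are already collected, and the sample size does not change.

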12.8 Analysis of Secondary Endpoint: Circulating Metabolic Biomarkers

Positively skewed variables will be log transformed prior to analyses. Graphical methods will be used in the first instance to show trends over time and differences between the intervention and control groups using box plots or line graphs. To test for differences between the intervention and control group, we will use two-sample *t*-tests with the assumption of unequal variance to compare baseline, 6, 12, and 24 month circulating inflammatory and energy metabolism biomarker levels, as well as mean changes and effect sizes in these measurements over the study period. Where differences are seen, these will be further investigated within the intervention group against compliance to exercise to demonstrate a dose response relationship. Biomarker assessment at baseline and 6 months are funded. Additional funding will be acquired for investigation of additional time points.

We will also calculate absolute changes in circulating inflammatory and energy metabolism biomarker levels, and use *t*-tests to test the null hypothesis that the average change in these measurements in the control and exercise groups is zero. We will use multivariate linear regression to examine the effect of the intervention on change in inflammatory and energy metabolism biomarker levels at 6, 12, and 24 months, adjusting for baseline levels. Additionally, to examine changes in metabolic biomarkers at various time points during the study period, we will utilise a mixed effects model with adjustment for baseline biomarker levels. Treatment assignment and time (6, 12, 24 months) and treatment × time interaction will be included as fixed effects. Biomarker assessment at baseline and 6 months are funded. Additional funding will be acquired for investigation of additional time points.

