2.0 OBJECTIVES

Primary Objective:

- 2.1** To determine if high intensity aerobic and resistance training plus psychosocial support increases overall survival compared to psychosocial support alone in patients with metastatic castrate-resistant prostate cancer.

Secondary Objectives:

- 2.2** To compare progression free survival between the intervention and control groups.
- 2.3** To compare the time to first occurrence of a symptomatic skeletal-related event between the intervention and control groups.
- 2.4** To compare time to progression of pain, degree of pain, and opiate use between the intervention and control groups.
- 2.5** To compare change in levels of inflammation, energy metabolism, and androgen metabolism biomarkers between the intervention and control groups over time.
- 2.6** To determine whether biomarkers of inflammation, energy metabolism, and androgen metabolism are associated with overall survival and explore the extent to which these biomarkers mediate the hypothesized association between exercise and overall survival.
- 2.7** To compare physical and emotional quality of life between the intervention and control groups

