4.4 Randomisation

After SCC approval, patients will be randomised in a 1:1 ratio to intervention (Supervised Exercise/SE) group or control (Self-directed Exercise/SDE) group, stratifying by treatment status at time of randomisation and study site. Randomisation will be performed through the study database but maintaining concealment from patients and recruiting staff, upon which time a Study ID will be assigned to the subject.

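### Section 12.8 adds zero-change tests and a baseline t-test that do not answer objective 2.5, and does not say which of its valid between-arm analyses carries the inference

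*Combined protocol and SAP*

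**What the plan says.** Objective 2.5 in Section 2.0 reads: "To compare change in levels of inflammation, energy metabolism, and androgen metabolism biomarkers between the intervention and control groups over time". Section 4.4 sets 1:1 randomisation.

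Section 12.8 lists these analyses, in this order:

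1. "To test for differences between the intervention and control group, we will use two-sample" t-tests with unequal variances. They cover levels at baseline, 6, 12 and 24 months, "as well as mean changes and effect sizes in these measurements over the study period".
2. A follow-on step: "Where differences are seen, these will be further investigated within the intervention group against compliance to exercise to demonstrate a dose response relationship".
3. In the next paragraph, as an addition, t-tests on absolute change to "test the null hypothesis that the average change in these measurements in the control and exercise groups is zero".
4. Regression: "We will use multivariate linear regression to examine the effect of the intervention on change in inflammatory and energy metabolism biomarker levels", adjusted for baseline.
5. A baseline-adjusted mixed model: "Treatment assignment and time (6, 12, 24 months) and treatment × time interaction will be included as fixed effects".

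The section says that only the baseline and 6-month assays are funded. It names no lead analysis, does not label item 3 as descriptive, and gives no significance level, standard deviation or sample size for the biomarkers.

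**The concern.** The tests in item 3 are most naturally read as a test against zero within each arm. A between-arm test of mean change is already in item 1, so that reading would make item 3 redundant. A within-arm change mixes any effect of exercise with time, disease course and systemic therapy, and its null hypothesis does not contain the treatment contrast. Section 8.2 itself expects a smaller rise in inflammation with exercise than with control, so change need not be zero in either arm. Sections 12.7, 12.9 and 12.10 plan no such within-arm test.

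The baseline t-test in item 1 compares arms formed by randomisation, so any difference it finds is due to chance. It also sits among the comparisons to which item 2 refers.

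With several tests of the same question and no order among them, the report could rest on whichever is significant. At stake are the clarity of a stated secondary objective and the false-positive rate of the biomarker findings.

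**Working it through.** **No plan figure to reproduce.** Section 12.8 gives no power, effect size or error rate. Assumed throughout: two-sided 5% tests. The figure of 412 per arm comes from Section 12.2, where it is the number evaluable for overall survival. It is used as a guide only, because the biomarker number is not stated.

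**A. Unranked between-arm tests at 6 months.** Suppose there is no intervention effect. Let the biomarker have SD 1 at both visits and baseline–follow-up correlation r (assumed). The tests of level, change and baseline-adjusted change are correlated but not identical. I simulated the chance that at least one is significant, with 412 per arm and 20,000 runs per setting:

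| r | any of the three significant |
|---|---|
| 0.3 | 8.9% |
| 0.5 | 9.7% |
| 0.7 | 10.2% |

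This is roughly 9–10% per biomarker, against 5% for one named test.

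**B. Baseline test and the trigger.** Under randomisation the baseline t-test rejects in 5% of trials per biomarker by construction (simulated 4.8–5.0%). If a difference seen means a significant result, and includes the baseline comparison, that is the chance of starting the dose-response work for no reason.

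**C. Within-arm significance, if it were used as evidence.** Let both arms have the same true change and let each within-arm test have power p. The arms are independent, so:

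- P(exactly one arm significant) = 2p(1−p), with maximum 2 × 0.5 × 0.5 = 50%.
- P(exercise significant, control not) = p(1−p), with maximum 25%.

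At 412 per arm, p = 0.5 needs a common change of about 1.96/√412 = 0.097 SD of change. With p from the noncentral t distribution:

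| Common change (SD of change) | Exactly one arm significant, 412 per arm |
|---|---|
| 0 | 9.5% |
| 0.05 | 28.6% |
| 0.097 | 50.0% |
| 0.15 | 24.2% |
| 0.20 | 3.6% |
| 0.30 | about 0% |

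With 200 per arm the peak moves: 41.2% at 0.10 SD, 49.3% at 0.15 SD and 31.6% at 0.20 SD. A simulation at 412 per arm and 0.097 SD gave 48.9% discordant and 24.8% exercise-only. Across common changes from 0 to 0.20 SD, the planned between-arm tests kept their level: 4.6–5.3% for the t-test on change and 4.4–5.1% for the baseline-adjusted regression.

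**D. Which analysis should lead.** Take a true between-arm difference of 0.2 SD, r = 0.5 and 412 per arm.

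- Unadjusted change: SD = √(2(1−0.5)) = 1. Noncentrality = 0.2/√(2/412) = 2.87, power 82%. The unadjusted level also has SD 1, so its power is the same.
- Baseline-adjusted: residual SD = √(1−0.5²) = 0.866. Noncentrality = 2.87/0.866 = 3.31, power 91%.

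**The case against.** The strongest reply is that objective 2.5 is already answered. Three between-arm analyses of change surround the zero-change sentence, and that sentence is offered as an addition, not as the test of the objective. This stands. A reader might infer that Section 12.8 analyses the objective with the wrong null hypothesis, but the text does not support that.

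A reader might also infer that up to half of null trials would report an effect. The documents do not support this either. Nowhere do they treat significance in one arm only as evidence, and the hypotheses in Section 8.2 on inflammation and insulin are explicitly comparative. The 50% counts both directions and needs a common change near 0.1 SD at full sample size. The documents give no SD or biomarker sample size from which to place this trial on that curve.

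Nor do the zero-change tests feed the dose-response step. The trigger follows the two-sample tests and comes before the zero-change sentence. The authors most likely meant a difference during follow-up, so the baseline trigger is a matter of literal wording.

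Finally, the baseline t-test does not bias the adjusted models, and whether each arm changed is a fair descriptive question. Both points are right, but a mean with its confidence interval answers the descriptive question without a test. The reply leaves untouched that the role of the zero-change tests is unstated and that no lead analysis is named.

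**Conclusion.** The point holds as a limited one. Section 12.8 contains valid analyses for objective 2.5, adds two kinds of test that do not bear on it, and leaves the basis for inference open. The firmest cost is the unranked testing: about 9–10% false positives per biomarker if any of the three 6-month tests is accepted, assuming two-sided 5% tests and baseline correlation of 0.3–0.7. The baseline trigger adds about a 5% chance per biomarker on a literal reading. The discordance figures, at most 50% in either direction and 25% for exercise only, are worst cases that depend on a misreading the protocol does not state. They are a reason to remove the temptation, not an error rate of the plan.

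**What to change.** In Section 12.8:

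- Delete the zero-change t-tests and the t-test of baseline levels. Show within-arm change as mean and confidence interval only.
- State that objective 2.5 is answered by the baseline-adjusted between-arm regression at 6 months, the funded time point. If later samples are assayed, the mixed model can take that role; with one post-baseline visit its treatment-by-time term cannot be estimated.
- Label the unadjusted t-tests as supportive.
- Tie the dose-response step to a between-arm difference in the named adjusted analysis.

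This costs a few sentences. It needs no new data, assays or patients, and under the assumptions in part D of the working the named analysis has more power than the unadjusted tests (91% against 82%).
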